5.5.2. Clinical Assessments

5.5.2.1. Lesion Counts

Non-inflammatory lesions (closed and open comedones), inflammatory lesions (papules, pustules, and nodules, if applicable) on the face, including the nose, and on the trunk (shoulders, upper back and upper anterior chest) will be counted and recorded separately at each scheduled site visit throughout the study.

Lesions are defined as follows:

Non-inflammatory lesions:

- Comedones – open (blackheads)
- Comedones – closed (whiteheads).

Inflammatory lesions:

- Papules – raised inflammatory lesions with no visible purulent material
- Pustules – raised inflammatory lesions with visible purulent material
- Nodules – any circumscribed, inflammatory mass greater than or equal to 5 mm in diameter with or without cystic changes.

The investigator/evaluator should use standard, good lighting and magnification as necessary to visualize lesions and a systematic counting procedure to ensure consistent and accurate counts.

The overall number of inflammatory lesions and non-inflammatory lesions for each of the two regions (face and trunk) will be reported separately in the eCRF. The overall number of total lesions

(inflammatory plus non-inflammatory lesions) will be calculated by the electronic data capture (EDC) system.

For the face, the total lesions will be calculated as the sum of inflammatory plus non-inflammatory lesions, including the nose.

For the trunk, the total lesions will be calculated as the sum of inflammatory plus non-inflammatory lesions of the anterior part of the trunk, excluding the neck and axillary regions.

Assessments per patient should be done by the same trained investigator throughout the study, if possible, to minimize the possibility for introduction of bias.

5.5.2.2. Investigator’s Global Assessment (IGA) (face)

The IGA scale to be used in the study is a measure of static evaluation of qualitative overall acne severity for face. IGA is an ordinal scale with 5 severity grades (reported only in integers, e.g., 0 to 4). Each grade is defined by a distinct and clinically relevant morphologic description to minimize inter-observer variability (**Table 2**). The grades on the scale have been sufficiently defined to appropriately and unambiguously represent each severity grade on the scale. The investigator is required to perform IGA scoring at each scheduled site visit. IGA scores will be documented in the eCRFs.

In case of worsening of acne, the investigator may consider treatment discontinuation according to section 8.3.1.

Table 2: IGA Scale For Acne Vulgaris*

Grade	Description	
0	CLEAR	Clear skin with no inflammatory or non-inflammatory lesions
1	ALMOST CLEAR	A few scattered comedones and a few small papules
2	MILD	Easily recognizable: less than half the face is involved. Some comedones and some papules and pustules
3	MODERATE	More than half of the face is involved. Many comedones, papules and pustules. One small nodule may be present
4	SEVERE	Entire face is involved. Covered with comedones, numerous papules and pustules. Few nodules may or may not be present

* Areas other than the face and nose are not included in assessment

Assessments per patient should be done by the same trained investigator throughout the study, if possible, to minimize the possibility for introduction of bias.

5.5.2.3. Physician Global Assessment (PGA) (trunk)

The PGA scale to be used in the study is a measure of static evaluation of qualitative overall acne severity for trunk. PGA is an ordinal scale with 5 severity grades (reported only in integers, e.g., 0 to

4). Each grade is defined by a distinct and clinically relevant morphologic description to minimize inter-observer variability (**Table 3**). The grades on the scale have been sufficiently defined to appropriately and unambiguously represent each severity grade on the scale. The investigator is required to perform PGA scoring at each scheduled site visit. PGA scores will be documented in the eCRFs. The areas defined for PGA assessment are shoulders, upper back and anterior chest which are accessible to self-application by the patient, i.e., the regions that the patient can easily reach and apply the study medication without assistance.

Table 3: PGA Scale For Acne Vulgaris

Grade	Description	
0	CLEAR	Clear skin with no inflammatory or non-inflammatory lesions
1	ALMOST CLEAR	A few scattered comedones and a few small papules
2	MILD	Easily recognizable: less than half the surface is involved. Some comedones and some papules and pustules
3	MODERATE	More than half of the surface is involved. Many comedones, papules and pustules. One small nodule may be present
4	SEVERE	Entire surface is involved. Covered with comedones, numerous papules and pustules. Few nodules may or may not be present

Assessments per patient should be done by the same trained investigator throughout the study, if possible, to minimize the possibility for introduction of bias.

5.5.2.4. Dermatology life quality index (DLQI/ C-DLQI)

Dermatology Life Quality Index (DLQI) (age 17 and older)/Children’s Dermatology Life Quality Index (C-DLQI) (for 16 years and younger) will be completed by each patient at Baseline and EoT. If the patient completed a CDLQI at the Baseline visit, a C-DLQI should be completed at the Week 12/ET Visit, regardless of the patient’s age at the Week 12/ET visit.

The DLQI/C-DLQI measures dermatology-related limitations of functional ability on patients’ lives. The questionnaires will be conducted prior to any acne assessment by the investigator, to avoid influencing the patient’s answers. The higher the score (ranging from 0 to 30), the more the QOL is impaired (Morgan M, 1997; Lewis-Jones MS 1995).

English master version of both questionnaires is in **Appendix F** (validated versions in local languages will be used). Authorization to use will be obtained.

5.5.2.5. [REDACTED]

[REDACTED]

[REDACTED]

[REDACTED]

[REDACTED]

Table 4: [REDACTED]

[REDACTED]	[REDACTED]	[REDACTED]
[REDACTED]	[REDACTED]	[REDACTED]

[REDACTED]

Assessments per patient should be done by the same trained investigator throughout the study, if possible, to minimize the possibility for introduction of bias.

[REDACTED] the following assessment will be done at V2-Day1 (baseline) and V5/Wk12, EoT:

[REDACTED]

[REDACTED] will be performed at the clinical site by a trained investigator for patients participating in the [REDACTED] portion of the study.

[REDACTED] be undertaken with regard to collection, transmission, storage and use of [REDACTED]. Collection of [REDACTED] is not mandatory; patients will be able to participate in the study even if they refuse to participate in [REDACTED] of patients will be obtained in [REDACTED]

The independent Third Party-Vendor [REDACTED] will perform the [REDACTED]

[REDACTED] will be performed in [REDACTED]

[REDACTED] **Methodology**

[REDACTED]

[REDACTED]

5.5.2.6. Local tolerability assessment

Local safety and tolerability will be evaluated on the basis of the following signs and symptoms:

Objective symptoms

- application site non-lesional erythema
- application site exfoliation
- application site dryness
- overall application site irritation.

Subjective symptoms

- stinging
- burning
- itching.

For all the site visits, objective symptoms (signs of erythema, exfoliation, dryness) will be assessed and scored by the Investigator and the patient will be questioned if he/she experienced any of the subjective symptoms (stinging, burning, itching) within the last 24 hours prior to visit.

During telephone contacts (patients aged 9 to < 12 only), patient will be questioned if he/she experienced any of the above sign/ symptoms within the last 24 hours prior to visit.

For each sign/symptom, a severity score will be assigned using a 4-point scale from 0 = none to 3 = severe (**Tables 5-7 and 9-11**).

Moreover, at baseline, the presence or absence of any of these signs/symptoms in the past 14 days will be collected.

The overall application site irritation will be assessed at baseline (only presence /absence assessment) and the end of study treatment (V5).

At V5, the overall application site irritation will be assigned using a 4-point scale from 0 = excellent to 3 = poor (see **Table 8**).

Only sign/symptom occurring after the first application of study medication that requires additional therapy or discontinuation of treatment or judged clinically significant by the Investigator, will be documented as a TEAE.

Table 5: Scoring of application site non-lesional erythema

Severity	Score	Description
None	0	No erythema
Mild	1	Light pinkness present
Moderate	2	Definite redness, easily recognized
Severe	3	Intense redness

Table 6: Scoring of application site exfoliation

Severity	Score	Description
None	0	No scaling
Mild	1	Barely perceptible shedding, noticeable only on light scratching or rubbing
Moderate	2	Obvious but not profuse shedding
Severe	3	Heavy scale production

Table 7: Scoring of application site dryness

Severity	Score	Description
None	0	No dryness
Mild	1	Slight barely perceptible fine superficial scale
Moderate	2	Clearly perceptible fine scale giving skin a powdery appearance
Severe	3	Marked roughness, cracked skin with fissures

Table 8: Scoring of overall application site irritation

Grades	Score	Description
Excellent	0	No signs of irritation during the study
Good	1	Slight signs of irritation during the study which might resolve by the end of the study
Fair	2	Signs of irritation throughout the study
Poor	3	Patient discontinued due to irritation
Irritation is defined as any sign or symptom of intolerance.		

Table 9: Scoring of stinging

Severity	Score	Description
None	0	No stinging
Mild	1	Slight sharp, tingling/stinging sensation; not really bothersome
Moderate	2	Definite sharp, tingling/stinging sensation; that was somewhat bothersome

Severe	3	Sharp, tingling/stinging sensation that had caused definite discomfort
--------	---	--

Table 10: Scoring of burning

Severity	Score	Description
None	0	No burning
Mild	1	Slight warm, burning sensation; not really bothersome
Moderate	2	Definite warm, burning sensation; that was somewhat bothersome
Severe	3	Hot, burning sensation that has caused definite discomfort

Table 11: Scoring of itching

Severity	Score	Description
None	0	No itching
Mild	1	Slight itching; not really bothersome
Moderate	2	Definite itching that was somewhat bothersome, without loss of sleep
Severe	3	Intense itching that had caused pronounced discomfort; night rest interrupted and excoriation of the skin from scratching might have been present

5.5.3. Measurement of safety parameters

Relevant medical history and AEs will be recorded.

Spontaneously noted complaints will be recorded along with their duration, intensity and probability of a correlation with the IMP (see Section 7.3, Evaluation of adverse events).

Laboratory examinations

The following laboratory parameters will be collected at screening (V1) and at the end of the comparative treatment phase (V5/Wk12, EoT) (see **Table 12**).

If clinically significant out of range or clinical significant values are found at V5, additional laboratory examinations will be performed at V6 (Follow-up/ETV visit).

Table 12: Laboratory examinations

Parameter	Screening examination V1 Day -14 to -1	Final examination V5 Wk12, Day 85 + 3 days (EoT)	ETV
Hematology			
RBC	X	X	X
WBC	X	X	X
Hemoglobin	X	X	X
Hematocrit	X	X	X

Parameter	Screening examination V1 Day -14 to -1	Final examination V5 Wk12, Day 85 + 3 days (EoT)	ETV
MCH	X	X	X
MCV	X	X	X
MCHC	X	X	X
Platelets	X	X	X
CBC/Differential	X	X	X
Clinical Chemistry			
AST (GOT)	X	X	X
ALT (GPT)	X	X	X
Total cholesterol	X	X	X
Triglycerides	X	X	X
HDL-C	X	X	X
LDL-C	X	X	X
Plasma glucose	X	X	X
████████████████████	X	X	X
████████	X	X	X
Pregnancy test	X	X	X
Fasting status	X	X	X

Hematology, clinical chemistry examinations and pregnancy test will be performed centrally.

Details on all laboratory procedures, collections, shipment of samples and reporting of results, alerting of extreme values and notable values by the central laboratory will be provided to investigators in the laboratory manual. The central laboratory will provide the sponsor with a copy of the laboratory certification and tabulation of the reference ranges. Details on collection and handling of laboratory samples are provided in the laboratory manual/instruction.

Any out of range laboratory results that are deemed clinically significant by the investigator will be recorded as medical history if detected at screening.

In case of unexpected laboratory out-of-range values in the blood samples collected at screening, which in the Investigator's opinion may pose the patient at increased risk during participation to the clinical trial, the patient/parents (or only one parent depending on local regulations) will be contacted to discontinue the treatment and will be withdrawn from the study. At all visits clinically significant laboratory results will be recorded as AEs.

5.5.4. Vital signs

Blood pressure and pulse rate will be measured at V1-screening, V2/Day 1 (only in case of V1 > 3 days before V2), V3/Wk4, V4/Wk8, V5/Wk12, ETV if applicable.

Blood pressure will be measured according to the National Institutes of Health, National Heart, Lung, and Blood Institute Guidelines [NIH 1997] with the following standardized techniques:

- patients are seated in a chair; blood pressure measurement begins after at least 10 minutes of rest

- the appropriate cuff size is used to ensure accurate measurement
- measurements will be taken with a sphygmomanometer.

Only one reading is required.

5.5.5. Appropriateness of measurements

Lesion count and IGA are widely used, non-invasive methods for examining overall acne severity. Both measures are described in the S-3 Guideline for Treatment of Acne (Nast A, 2016) and the FDA Draft ‘Guidance for Industry - Acne Vulgaris: Developing Drugs for Treatment’ (May 2018).

Investigators global assessment and PGA scores have been used in clinical studies of truncal acne in patients presenting with acne on the trunk and face, (Del Rosso J.Q, Hoffman L.K, 2018) and in addition, the PGA was used to assess efficacy in 2 recent registration studies that resulted in Food and Drug Administration's approval of trifarotene (Tan J, 2019; Blume-Peytavi 2020), indicating the current Food and Drug Administration endorsement of the PGA as an appropriate clinician-reported outcome measure for truncal acne in clinical trials.

Assessments should be conducted by investigators who are experienced and have been trained on the use of these evaluation tools. Assessments per patient should be done by the same trained investigator throughout the study, if possible, to minimize the possibility for introduction of bias.

The use of quality of life and psychosocial questionnaires is considered essential to adequately understanding just how the disease is affecting the patient, and to better understand the progress of the disease and the acne impact on QoL can drive the choice of therapy by clinicians (S-3 Guideline for Treatment of Acne, Nast A 2016; Simpson NB, 2004).

5.5.6. Primary efficacy variable

There are two primary efficacy variables: lesion count and IGA.

The primary variables are chosen in accordance with the S-3 Guideline for Treatment of Acne (S-3 Guideline for Treatment of Acne, Nast A 2016) and the FDA Guidance for industry. Acne vulgaris: developing drugs for treatment (May 2018). Experience with topical anti-acne medication has shown that a 12-week treatment period is in general sufficient to demonstrate efficacy. Thus, Wk12 (V5) should be suitable for the evaluation of the primary endpoints.

6. Data analysis and statistics

The statistical evaluation will be performed using the software program SAS (Statistical Analysis System, SAS, Cary, NC).

Based on the following description of statistical methods a detailed statistical analysis plan will be generated and finalized prior to database closure.

6.1. Generation of data base

Data from the source documents will be captured in an eCRF by a software package that can be customized for remote data entry procedure and that maintains an electronic audit trail. Only authorized site personnel will be able to enter/modify/correct data to the eCRF. The investigator/coordinator or designee must enter the information required by the protocol as soon as possible after the visit into the eCRF. The data will be checked for consistency. Queries for discrepant data may be generated automatically by the system upon entry or generated manually by the monitor or the trial data manager. All queries, generated by the system or by a user, will be electronic. All data management procedures will be detailed in a separate, specifically identified file that collectively will be referenced as the data management plan (DMP). The database structure will be validated by the vendor. The eCRFs will be developed in the EDC system in accordance with vendor standard operating procedures (SOPs) under supervision in agreement with the Sponsor. Once all the queries are closed and Data Management has verified the data, the Investigator will sign the eCRF (eSignature), and the database will be locked.

AEs and medical history will be coded with MedDRA (MedDRA version will be defined in the DMP); previous and concomitant therapy will be coded according to ATC. In case of general discontinuation of a specific treatment the common terminology criteria for adverse events (CTCAE) classification will be used and documented in the respective eCRF section as free text.

Patient data generated from the eCRF in portable document format (PDF) will be provided to the site at the end of the trial.

6.2. Analysis sets and type of analysis

Screened Analysis Set (SCR)

This analysis set includes all patients who signed the informed consent form and received a screening number, regardless of whether they completed all the screening procedures.

Enrolled Set (ENR)

All patients included in the study, excluding screening failure.

Randomized Set (RND)

All enrolled patients who are randomized to a treatment arm.

Full Analysis Set (FAS)

The Full Analysis Set (FAS) includes all randomized patients who receive at least one dose of the study medication and have at least one valid post-baseline efficacy assessment for both primary endpoints.

The analyses on FAS will be performed with the Intention-To-Treat (ITT) principle.

Per-Protocol Set (PPS)

The Per-Protocol Set (PPS) comprises all patients included in the FAS who complete the study without major protocol deviations. Major protocol deviation will be identified in the SAP and/or during a blind medical review.

The analysis of efficacy will be conducted on the FAS and PPS sets, with the FAS considered as the primary set for statistical analysis, based on treatment as randomized.

Safety Set (SS)

The Safety Set (SS) includes all patients who received at least one dose of study treatment. Safety analyses will be performed on the Safety Set based on treatment as received.

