Clinical trial protocol

GEDACNE-1 STUDY

A phase III study to assess efficacy and safety of N-Acetyl-GED-0507-34-LEVO gel ■%, applied once daily for 12 weeks in patients with acne vulgaris (GEDACNE-1)

[figure not shown]
Confidential

**PPM Services S.A
[name]**

This clinical trial protocol is the property of PPM Services S.A., a Nogra Group Company.
It may not be reproduced, distributed or otherwise used.

Synopsis

Sponsor	PPM Services S.A., Switzerland
Trial no.	NAC-GED-0507-ACN-01-23-A
EU CT No.	2023-510339-12-00
Title	A phase III study to assess efficacy and safety of N-Acetyl-GED-0507-34-LEVO gel █%, applied once daily for 12 weeks in patients with acne vulgaris (GEDACNE-1)
Phase	Phase 3 (Pivotal)
International coordinating investigators	[name] [name]
Study centers	At least 40 sites, located in at least 4 European countries will participate in this study.
Study period (planned)	Q3-2024 – Q2-2026. Duration of patient participation is approximately 16 weeks (14-day screening and 12 weeks of treatment +2 weeks of follow-up) and will require up to 6 visits (V). The planned duration of recruitment, from First Patient In (FPI) to Last Patient In (LPI), is approximately 10 months.
Objective(s)	The objective of the study is to evaluate the efficacy and the safety of N-Acetyl-GED-0507-34-Levo █% gel [IMP 1], in comparison to the corresponding vehicle gel [IMP 2-V], applied once daily (OD) for 12 weeks in patients with acne vulgaris.
Study design	Multicenter, randomized, parallel-group, vehicle-controlled, double-blind efficacy and safety study.

Number of patients (planned)	Four Hundred (400) patients will be recruited, to obtain at least 366 patients in the full analysis set (FAS). Patients will be randomly allocated to one of the two treatment arms (IMP 1 or IMP 2-V) in a 1:1 ratio: 200 patients in the IMP 1 arm and 200 patients in the IMP 2-V arm.
DSMB	A Data Safety Monitoring Board will be established to undertake periodic risk-benefit assessments during the clinical trial; the appropriate written charter prescribes its establishment and management.
Study medication/ Investigational medicinal product (IMP)	IMP 1 arm N-Acetyl-GED-0507-34-Levo ■% gel (■ mg/100 mg), PPM Services S.A., Switzerland IMP 2/Vehicle arm (V) N-Acetyl-GED-0507-34-Levo corresponding vehicle, PPM Services S.A., Switzerland

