5.1. Overall trial design and plan - description

This is a multicenter, randomized, parallel-group, vehicle-controlled, double-blind, efficacy and safety study. At least 40 sites located in at least 5 European countries will participate in this trial.

[figure not shown]
Approximately 400 patients (males and female aged ≥ 9 and <50 years) affected by facial acne vulgaris are planned to be randomized in order to have at least 366 patients in the full analysis set (FAS) and will be randomly allocated to one of the 2 treatment arms (NAC-GED-0507-34-Levo ■% gel, or vehicle gel) in a 1:1 ratio. Recruitment will be competitive between the sites.

Stratified randomization will be conducted to guarantee the followings:

- Subset 9 to < 12 years: 5% of patients, corresponding to 20 patients.

The trial design consists of a 14-day screening period, a 12-week comparative treatment period, and a 2-week treatment-free follow-up period. Each patient will have 6 visits: V1-screening, V2-Day 1, V3/Wk4-Day 29, V4/Wk8-Day 57, V5/Wk12-Day 85 (EoT) (primary endpoint visit), V6/Wk14-Day 99 safety follow-up visit (Phone contact). Patients who complete 12 weeks of treatment can be eligible to continue treatment with NAC-GED-0507-34-Levo gel ■%, in a separate open-label long-term study NAC-GED-0507-ACN-01-23-LT (GEDACNE-LT). In this case, the V6/Wk14-Day 99 follow-up visit (Phone contact) will not be performed. (**Figure 1**). Additionally, two telephone contacts will be performed in 9 to < 12 years old patients, at Wk2 and Wk10.

Figure 1- Study design

IMP will be topically applied OD by the patient to the entire face (including nose; avoiding eyelid and lip region) and to skin areas of the trunk accessible for self-application (shoulders, upper back, and upper anterior chest) if those are affected by acne. The study medication is applied by patients at home, except for the first dose, which will be applied at the site (V2, Day 1) under the Investigator's or study nurse's supervision. The gel will be applied to dry and, cleansed skin at night, following the instructions received at the site by the Investigator/study nurse on the correct method of IMP application.

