6.5. Rationale for the sample size

The sample size is based on the two co-primary endpoints: relative change from baseline in total lesion count on the face (inflammatory plus non-inflammatory) and IGA success at V5/Wk12 to reach a power of 90% at a level of 0.05, since this are considered the most relevant clinical endpoints.

The formal calculation of sample size is based on the paper from T. Sozu et al. Sample size for co-primary continuous and binary endpoint (2012), assuming the normality of the relative change from baseline distribution and making the following assumptions:

- an error I type of ■%
- a statistical power of ■%
- a relative change from baseline in total lesion count on the face at V5/Wk12 in the IMP 2-V arm (placebo arm) of ■% (data retrieved from the Study NAC-GED-0507-ACN-01-18)
- a Standard Deviation (SD) of the difference between treatment arms of ■% (data retrieved from the Study NAC-GED-0507-ACN-01-18).
- a rate of IGA success on the face at V5/Wk12 in the IMP 2-V arm (placebo arm) of ■% (data retrieved from the Study NAC-GED-0507-ACN-01-18)
- a difference between the two treatment arms in terms of the relative change from baseline in total lesion count on the face (inflammatory plus non-inflammatory) at V5/Wk12 equal to or greater than ■% and a difference in IGA successes equal or greater than ■% (data retrieved from the Study NAC-GED-0507-ACN-01-18).

A sample size of 366 evaluable patients (183 in each treatment arm), will be adequate to find a significant difference between the two treatment arms in terms of the relative change from baseline in total lesion count on the face (inflammatory plus non-inflammatory) at V5/Wk12 and in IGA successes.

Considering a drop-out rate close to ■% of non-evaluable patients for any reason, a total of 400 patients will have to be enrolled in the study (sample allocation ratio 1:1).

A second pivotal Phase 3 study (NAC-GED-0507-ACN-01-23-B) with an identical study design to the present study is planned to be performed with an equivalent sample size of 400 patients in total.

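### The primary efficacy set leaves out randomised patients with no post-baseline assessment of both endpoints, which conflicts with the stated ITT principle and treatment policy strategy

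*Protocol*

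**What the plan says.** Section 6.2 of the protocol, and the analysis sets in the synopsis, define the FAS as randomised patients who received at least one dose and who "have at least one valid post-baseline efficacy assessment for both primary endpoints". Section 6.2 then states: "The analyses on FAS will be performed with the Intention-To-Treat (ITT) principle". Efficacy is analysed on the FAS and the Per-Protocol Set (PPS), "with the FAS considered as the primary set for statistical analysis, based on treatment as randomized".

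Section 6.6.1.1 names the FAS within the target population of both primary estimands. It applies a treatment policy strategy to treatment discontinuation, study withdrawal and prohibited medication, and uses LOCF for data missing for whatever reason. The sensitivity analyses in section 6.6.1.3 use the PPS, which is a subset of the FAS, and multiple imputation within the FAS. The synopsis assigns only baseline and demographic summaries to the Randomized Set.

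The synopsis and section 5.1 plan for 400 randomised patients to yield at least 366 in the FAS. Section 6.5 allows for a redacted proportion "of non-evaluable patients for any reason, a total of 400 patients will have to be enrolled in the study".

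**The concern.** The first scheduled post-baseline efficacy visit is Week 4. The first dose is applied at the site at Visit 2, the day of randomisation, so the dosing condition should remove almost nobody. The post-baseline condition does the excluding.

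Whether a patient meets that condition is decided after randomisation and may depend on treatment. Sections 5.4.7 and 8.3.1 list treatment-linked routes out of the trial: adverse events, local or allergic reactions, permanent stopping of the gel for any reason, and a need for other acne treatment. If exclusion differs between arms and is related to outcome, the FAS comparison is biased for both co-primary endpoints.

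The plan also disagrees with itself. Under the estimand, a patient who withdraws after Week 4 is kept and handled by LOCF. A patient with the same event before any assessment leaves the population altogether. The rule for data missing for whatever reason therefore never reaches the patients with the most missing data. This is not a detail left to a later analysis plan, because the protocol fixes both the set and the estimands.

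**Working it through.** **1. Who is excluded.** Section 6.3 schedules lesion count and IGA at Weeks 4, 8 and 12 and at any early termination visit. A dropout assessed at any of these stays in the FAS. Section 5.5.1 calls for a termination visit after discontinuation during treatment, but section 8.3.1 requires its procedures only where feasible. Those lost are patients with none of these assessments. Missing only one of the two endpoints throughout is mostly theoretical, because Appendix A schedules both at the same visits.

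**2. The plan's own allowance.** 400 − 366 = 34, and 34/400 = 8.5%. Checking back, 366/(1 − 0.085) = 400. The pair is consistent, but the 8.5% is derived from it because the stated rate is redacted. The 366 cannot be rebuilt, since its effect sizes, SD and vehicle rates are also redacted.

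**3. Effect on the IGA difference (E2).** Assumptions: FAS success of 45% vs 24%, lying between the Phase 2b subgroup rates in the synopsis (41.4% and 50.8% active; 20.9% and 28.8% vehicle); all 34 places used; every excluded patient a non-success.

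Rate among all randomised = FAS rate × (200 − excluded)/200.

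| Excluded, active/vehicle | Active | Vehicle | Difference (FAS: 21.0) |
|---|---|---|---|
| 17/17 | 0.45 × 183/200 = 41.2% | 0.24 × 183/200 = 22.0% | 19.2 |
| 24/10 | 0.45 × 176/200 = 39.6% | 0.24 × 190/200 = 22.8% | 16.8 |
| 10/24 | 0.45 × 190/200 = 42.8% | 0.24 × 176/200 = 21.1% | 21.6 |

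**4. Effect on relative lesion change (E1).** Illustration with the Phase 2b means for patients aged 18 or under (−59.0% vs −33.4%, a difference of 25.6 points), with excluded patients set to 0% change:
- 17/17: 25.6 × 183/200 = 23.4.
- 24/10: 59.0 × 0.88 − 33.4 × 0.95 = 51.9 − 31.7 = 20.2.
- 10/24: 59.0 × 0.95 − 33.4 × 0.88 = 56.1 − 29.4 = 26.7.

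**5. Type I error of the IGA chi-square test on the FAS.** Assume no true effect: 25% success (50 of 200) in each randomised arm, with all excluded patients failures. FAS rates are 50/(200 − excluded), and d is their difference. The rejection rate is Φ((d − 1.96·se₀)/se₁) + Φ((−d − 1.96·se₀)/se₁), where se₀ is the pooled and se₁ the unpooled standard error.
- 17/17: d = 0; rejection 0.050.
- 22/12: d = 50/178 − 50/188 = 0.015; rejection 0.062.
- 25/9: d = 50/175 − 50/191 = 0.024; rejection 0.081.

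The mirror splits give the same two-sided rates, with the false signal favouring vehicle. These rates are for the IGA test alone. If success requires both endpoints, the joint rate cannot be higher.

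**6. Cost in sensitivity to a real effect.** With 41.4% vs 20.9% in the FAS, the chi-square z is 4.23 on the FAS and 4.16 on all 400 (17/17), or 4.25 and 3.62 (25/9).

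**The case against.** The strongest reply concerns size and direction, and most of it stands.

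- A reader might infer that early dropouts as a group are excluded. They are not: anyone with a Week 4 or termination assessment stays in and is carried forward.
- A reader might take 34 as a forecast. It is the most that the target of at least 366 allows, and it covers non-evaluability of any kind.
- A reader might infer that the FAS favours the active gel. The documents do not show this. Leaving for lack of benefit would more plausibly remove vehicle patients, and the 10/24 split makes the FAS slightly conservative. Phase 2b adverse event rates were 19% and 16% in the two active arms and 19% on vehicle (section 3.2), which does not suggest heavier loss on active.
- Nor do the documents show that the excluded patients are mostly treatment failures. Leaving early without a visit may be simple loss to follow-up. The fall to 19.2 points at 17/17 is dilution from counting them all as failures, and type I error there stays at 0.050.
- The set is named FAS, not ITT, and it does analyse patients as randomised.

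The inconsistency remains. The protocol claims the ITT principle for a set conditioned on follow-up, and no planned efficacy analysis would show whether the exclusion mattered.

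**Conclusion.** The point holds as an inconsistency in the primary analysis set and estimands, with a possible bias of uncertain size and direction. The exclusion follows directly from the text. The magnitude rests on assumptions: the full 34 excluded, assumed success rates, all excluded patients counted as failures, and chosen splits. On those terms the all-randomised IGA difference lies between 16.8 and 21.6 points, against 21.0 in the FAS. Type I error for the IGA test is between 0.050 and 0.081 over the splits shown. The firmer claim that the protection of randomisation is lost goes too far: at most 8.5% are affected, and bias needs exclusion that is both unequal and related to outcome. The change is still worth making before unblinding, because this is a pivotal trial and section 6.5 plans a second one of identical design.

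**What to change.** 1. In section 6.2 and the synopsis, make the already defined Randomized Set, analysed as randomised, the primary set for E1 and E2.
2. For patients with no post-baseline data, count E2 as non-success and set E1 to no change from baseline. This is baseline carried forward, in line with the stated LOCF. The two rules agree, because section 5.3.3 requires a baseline IGA of at least 2 and success needs 0 or 1.
3. Extend the multiple imputation analysis in section 6.6.1.3 to all randomised patients, so that the carried-forward values are tested under a different assumption.
4. Keep the current FAS as a supportive analysis.
5. Delete the Full Analysis Set from the population attribute of the primary and sensitivity estimands, leaving the population defined by patient characteristics.
6. Make the same change in the planned second study if its text matches.

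Cost: this is more than wording, since it adds a rule to the missing-data method in sections 6.6.1.1 and 6.7. The estimated effect may be slightly smaller. The sample size does not change, as the 400 already planned would all be analysed.
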